18.2.2 Missing dates handling

Start and end dates of CS medications will be imputed following the same rules as defined for the previous and concomitant medications (see Section 9.10).

18.2.3 Conversions

The tables below provide conversions to be performed in order to assess the CS dosage:

Table 6: Conversion factors in prednisone equivalent

Who-drug Term	Conversion factor in prednisone equivalent
METHYLPREDNISOLONE	1,25
METHYLPREDNISOLONE SODIUM / METHYLPREDNISOLONE SODIUM SUCCINATE	1.25
METHYLPREDNISOLONE ACETATE	1.25
HYDROCORTISONE / HYDROCORTISONE SODIUM SUCCINATE	0.25
BETAMETHASONE	6.667
BETAMETHASONE DIPROPIONATE	6.667
BETAMETHASONE VALERATE	6.667
BETAMETHASONE PHOSPHATE	6.667
DEXAMETHASONE	6.667
TRIAMCINOLONE / TRIAMCINOLONE ACETONIDE	1.25
CORTISONE	0.2
PREDNISOLONE	1
PREDNISONE	1
DEFLAZACORT	0.83333
MEPREDNISONE	1,25
PARAMETHASONE	2,5
CRONOLEVEL	6.667
BETROSPAM	6.667

CONFIDENTIAL

Table 7: Frequency conversions for CS

Frequency	Conversion factor	Numerical Conversion factor
OAM	1/30	0.0333
QOD	1/2	0.5000
QW	1/7	0.1429
QWK	1/7	0.1429
BID/Q12	2	2.0000
TID/Q8	3	3.0000
QD – including QD with AM or PM (e.g. QD(AM), QD(PM), QD at AM, QD at PM)	1	1.0000
ONCE	1	1.0000
QAM	1	1.0000
Q2H	12	12.0000
Q3H	8	8.0000
Q4H	6	6.0000
Q6H	4	4.0000
Q8H	3	3.0000
Q12H	2	2.0000
Q24H	1	1.0000
QHS	1	1.0000
QID/Q6	4	4.0000
QPM	1	1.0000
QH	24	24.0000
Q3W	1/21	0.0476
Q3D	1/3	0.3333
TIW or Three times a week	3/7	0.4286
Four times a week	4/7	0.5714
Q4W, every 4 weeks	1/28	0.0357
BIW or Twice a week	2/7	0.2857
EVERY 3 HOURS	8	8.0000
X1	1	1.0000
EVERY OTHER DAY	1/2	0.5000
EVERY OTHER DAY ALTERNTATLY WITH30 MG Q0D	1/2	0.5000
EVERY OTHER DAY ALTERNTATLY WITH 20 MG QOD	1/2	0.5000
ONCE A WEEK, 1 TIME PER WEEK	1/7	0.1429
QD (EVERY MORNING)	1	1.0000
SINGLE DOSES	1	1.0000
ALTERNATE DAYS	1/2	0.5000
TWO TIMES A DAY	2	2.0000
4 DOSES GIVEN EVERY 2ND DAY	2	2.0000

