The Medical Monitor and the EAC will review CS use and Medical Monitors will follow-up with the site for further discussions of all cases where there has been no decrease in CS dosing in participants who appear to be improving and/or maintaining an improvement of disease activity.

Table 10 Prednisone-equivalence Calculation (Total Daily Dose)

Medication	Equivalent (mg) to 1 mg of Prednisone
Betamethasone	0.15
Cortisone	5
Dexamethasone	0.15
Deflazacort	1.2
Hydrocortisone	4
Meprednisone	0.8
Methylprednisolone	0.8
Prednisolone	1
Triamcinolone	0.8

Non-systemic corticosteroids

From Screening to Week 24 of the DBPC treatment period, generally, there are no restrictions on non-systemic CS dosage (defined as optic, otic, intranasal, stable inhaled, and ophthalmic); For topical CS use, see Permitted medicines, and prohibited medicines.

Topical Corticosteroids Class and Cross-reactivity

Topical CS Class II–VII applied for > 4 weeks, or > 2 times per day or use of topical CS Class I or augmented betamethasone dipropionate 0.05% gel or ointment are not allowed. (Reference: https://emedicine.medscape.com/article/2172256-overview).

 Table 11
 Topical Corticosteroids Class

Potency Class		Medication			
		Clobetasol propionate 0.05%			
Super potent	I	Diflorasone diacetate 0.05%			
		Amcinonide ointment (0.1%)			
		Betamethasone dipropionate ointment (0.05%)			
	II	Desoximetasone (cream or ointment) (0.025%)			
		Fluocinonide (cream, ointment, or gel) (0.05%)			
High potency		Halcinonide cream (0.1%)			
		Betamethasone dipropionate cream (0.05%)			
		Betamethasone valerate ointment (0.1%)			
	III	Diflorasone diacetate cream (0.05%)			
		Triamcinolone acetonide ointment (0.1%)			
		Desoximetasone cream (0.05%)			
	10.7	Fluocinonide acetonide ointment (0.025%)			
	IV	Hydrocortisone valerate ointment (0.2%)			
		Triamcinolone acetonide cream (0.1%)			
Madarata natanay		Betamethasone dipropionate lotion (0.02%)			
Moderate potency		Betamethasone valerate cream (0.1%)			
	V	Fluocinonide acetonide cream (0.025%)			
	V	Hydrocortisone butyrate cream (0.1%)			
		Hydrocortisone valerate cream (0.2%)			
		Triamcinolone acetonide lotion (0.1%)			
		Betamethasone valerate lotion (0.05%)			
	VI	Desonide cream (0.05%)			
Low potency		Fluocinolone acetonide solution (0.01%)			
Low polericy		Dexamethasone sodium phosphate cream (0.1%)			
	VII	Hydrocortisone acetate cream (1%)			
		Methylprednisolone acetate cream (0.25%)			

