Attributes of the estimands are described in the table below:

Endpoint	Clinically meaningful CS reduction, defined as reduction of daily prednisone-equivalent dose from ≥ 10 mg at Day 1 to ≤ 5 mg by the Week 12 visit and sustained through Week 24
Population(s)	 SLE participants (Cohort B) with daily prednisone-equivalent dose ≥ 10 mg at Day 1 Cohort A participants with daily prednisone-equivalent dose ≥ 10 mg at Day 1
Treatment	Enpatoran vs placebo
Population-level summary measure	Odds ratio (conditional on stratification factors) between each active dose and placebo

Clinically meaningful CS reduction at Week 12 will be assessed based on the "CORTICOSTEROID MEDICATION DETAILS" form. Sustainment of the reduction will be assessed throughout the period between Week 12 and Week 24 (see appendix 18.2 for derivation of daily prednisone-equivalent dose).

A composite estimand strategy will be applied to handle the intercurrent events. Participants who experience any of these intercurrent events will be considered as not achieving CS reduction.

Descriptive Analysis

The number and percentage of participants with a clinically meaningful CS reduction will be provided.

Inferential Analysis

A logistic regression of clinically meaningful CS reduction status (yes/no) on the study intervention groups as a categorical variable and the stratification factors (see Section 14) will be fitted.

Odds ratios together with their 95% CI will be provided for each enpatoran group vs placebo. Treatment effect (and 95% CI) on the probability scale will also be provided.

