LLDAS attainment will be summarized using descriptive statistics (frequency and percentage) at each on-treatment scheduled visit. Additionally, a line plot depicting the percentage of responders over time grouped by study intervention group will also be provided.

Inferential analysis

A logistic regression of LLDAS attainment (yes/no) at Week 24 on the study intervention groups as a categorical variable and the stratification factors will be fitted.

Odds ratios together with their 95% CI will be provided for each enpatoran group vs placebo. Treatment effect (and 95% CI) on the probability scale will also be provided.

INFORMATION

14.3.8 Remission Attainment through Week 24

This analysis will be conducted at the final analysis. Attributes of the estimand are described in the table below.

Endpoint	Remission attainment at Week 24
Population(s)	SLE participants (Cohort B)
Treatment	Enpatoran vs placebo
Population-level summary measure	Odds ratio (conditional on stratification factors) between each active dose and placebo

Remission attainment per 2021 DORIS definition (Vollenhoven 2021) is defined at a specific visit as meeting the following criteria at the visit:

- · CCI
- PGA of SLE < 0.5 (0-3 scale)
- Daily prednisolone-equivalent dose ≤ 5 mg from the day after the previous visit until the day of the current visit (see appendix 18.2 for derivation of daily prednisone-equivalent dose). If the previous visit is missed, the daily prednisolone-equivalent dose should be below or equal to 5 mg from 27 days prior to the current visit until that visit.
- Stable immunosuppressives including biologics

This criterion will not be specifically programmed but is covered via the handling of the intercurrent event "protocol-prohibited medications as determined by EAC".

Imputation for CCl is described in section 9.11.2 and section 9.11.4 respectively. If at least one criterion for remission is not evaluable at a visit, remission will be considered as non-attained at the visit.

Descriptive Analysis

Remission attainment will be summarized using descriptive statistics (frequency and percentage) at each on-treatment scheduled visit. Additionally, a line plot depicting the percentage of responders over time grouped by study intervention group will also be provided.

Inferential analysis

A logistic regression of remission attainment (yes/no) on the study intervention groups as a categorical variable and the stratification factors will be fitted.

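### Rounded prednisone-equivalence factors in SAP Table 6 put a few exact boundary doses of deflazacort, dexamethasone and betamethasone on the wrong side of the corticosteroid cut-offs

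*SAP*

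**What the plan says.** Protocol Appendix 7, Table 10, is headed "Equivalent (mg) to 1 mg of Prednisone", so the prednisone equivalent is the dose divided by the table value. Its entries include "Deflazacort 1.2", "Dexamethasone 0.15" and "Betamethasone 0.15".

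SAP section 18.2.3, Table 6, gives multipliers instead: "DEFLAZACORT 0.83333" and "DEXAMETHASONE 6.667", with 6.667 for betamethasone too. Table 7 gives dosing-frequency factors in two columns, one of fractions and one of four-decimal values. Section 18.2.4 builds the daily dose from these conversions and sums over drugs. Nothing in 18.2 mentions rounding or a tolerance.

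The resulting dose meets inclusive cut-offs:

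- Corticosteroid reduction (SAP 14.3.3), also part of the combined BICLA endpoint (14.3.4): "reduction of daily prednisone-equivalent dose from ≥ 10 mg at Day 1 to ≤ 5 mg by the Week 12 visit", sustained to Week 24. Both populations are limited to participants at 10 mg or more on Day 1.
- Remission (14.3.8): "Daily prednisolone-equivalent dose ≤ 5 mg from the day after the previous visit until the day of the current visit".
- LLDAS (14.3.7): the same kind of rule at 7.5 mg.
- Baseline corticosteroid subgroup (8.2): high means 10 mg or more, low/medium means less.
- Baseline dose categories (section 12): boundaries at 5, 7.5, 10, 15 and 20 mg.

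**The concern.** A rounded factor is harmless almost everywhere, but at an inclusive cut-off an error in the fifth significant figure turns a yes into a no. Two participants with the same steroid exposure by the protocol's table could then be classified differently only because their drugs differ.

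At the 10 mg cut-off, a participant would lose membership of two analysis populations and move to the other baseline subgroup. At the 5 and 7.5 mg cut-offs, a participant who met the dose condition would be scored as not meeting it. The groups concerned can be small: Cohort A plans 25 per arm, the corticosteroid-reduction analysis uses only those at 10 mg or more, and SAP 8.2 runs a Cohort A subgroup analysis only if each level has at least 5 participants in every arm (10 in Cohort B).

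**Working it through.** **Inputs.** Protocol Table 10: deflazacort 1.2 mg, dexamethasone 0.15 mg and betamethasone 0.15 mg, each equal to 1 mg prednisone. SAP Table 6: 0.83333 and 6.667. Cut-offs: as listed from SAP 14.3.3, 14.3.4, 14.3.7, 14.3.8, 8.2 and section 12.

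**Step 1: reproduce the SAP factors.** Factor = 1 / Table 10 value.

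- Deflazacort: 1/1.2 = 0.833333…, printed as 0.83333 (rounded down).
- Dexamethasone, betamethasone: 1/0.15 = 6.666666…, printed as 6.667 (rounded up).

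Both are correct rounded inverses. The other Table 10 drugs have exact inverses in Table 6: cortisone 0.2, hydrocortisone 0.25, methylprednisolone, meprednisone and triamcinolone 1.25, prednisolone 1.

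**Step 2: apply them at the boundary.** Boundary dose = cut-off × Table 10 value. SAP dose = boundary dose × Table 6 factor.

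| Drug | Cut-off (mg) | Boundary dose (mg) | SAP dose (mg) | Result |
|---|---|---|---|---|
| Deflazacort | ≤ 5 | 6 | 4.99998 | right |
| Deflazacort | ≤ 7.5 | 9 | 7.49997 | right |
| Deflazacort | ≥ 10 | 12 | 9.99996 | **wrong** |
| Dexamethasone, betamethasone | ≤ 5 | 0.75 | 5.00025 | **wrong** |
| Dexamethasone, betamethasone | ≤ 7.5 | 1.125 | 7.500375 | **wrong** |
| Dexamethasone, betamethasone | ≥ 10 | 1.5 | 10.0005 | right |

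The direction of the rounding decides which cut-off is missed: a factor rounded down fails a lower limit, and a factor rounded up fails an upper limit. In the baseline categories, deflazacort 18 mg (18 × 0.83333 = 14.99994) and 24 mg (24 × 0.83333 = 19.99992) likewise fall one category too low.

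**Step 3: Table 7.** With the fraction column the boundary cases are exact. With the four-decimal column the same kind of error appears and reaches prednisone itself: 35 mg weekly × 0.1429 = 5.0015 (exact value 35/7 = 5), and 30 mg every third day × 0.3333 = 9.999 (exact value 30/3 = 10). These regimens illustrate the arithmetic; they are not taken from the documents.

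**Step 4: after the change.** Dividing by 1.2 or 0.15, or rounding the Step 2 products to two decimals, returns exactly 5, 7.5 and 10 mg in all six rows. Rounding alone would not repair every decimal in Table 7: the 1/30 factor printed as 0.0333 gives 300 × 0.0333 = 9.99, which stays below 10. The fraction column therefore has to be named as well.

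**The case against.** The strongest reply is that the factors are correctly rounded, that a programmer may round before comparing, and that what is missing is only a precision rule. That stands in part. But the SAP's rule, applied as written, gives a classification that contradicts protocol Table 10, and a prespecified rule should not depend on an unstated step. The SAP does set precision conventions where it considers them necessary, for example for pharmacokinetic data in 16.1.1 and 16.1.2.

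Several wider readings are tempting, and the documents do not support them:

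- *Every dose equal to 5, 7.5 or 10 mg is misclassified.* Half of the rows in Step 2 fall on the right side, and daily doses of prednisone, prednisolone, methylprednisolone and the other exactly converted drugs do not move.
- *Table 7 misclassifies too.* It already prints the exact fractions. The error arises only if the decimal column is programmed, and the SAP does not say which column is used.
- *The protocol taper drives participants onto these boundaries.* The example schedules in protocol Table 9 are in prednisone and methylprednisolone, which convert exactly. The 10 mg test applies at Day 1, before tapering starts at Week 2. The 7.5 mg limit lies above the taper target of 5 mg or less, so it matters for LLDAS at Week 24 only for someone still above that target.
- *The primary results are at risk.* No visible BICLA or CLASI-A criterion uses these cut-offs, although the intercurrent-event text is redacted. Secondary p-values are nominal (protocol 9.4).

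**Conclusion.** The point holds, within narrow limits. As written, the SAP misclassifies deflazacort at exactly 10 mg prednisone equivalent, and dexamethasone or betamethasone at exactly 5 and 7.5 mg. The first removes the participant from the populations of 14.3.3 and 14.3.4 and places them in the low/medium subgroup. The second makes a participant fail corticosteroid reduction and remission (5 mg) or the dose condition of LLDAS (7.5 mg). Deflazacort boundary doses at 15 and 20 mg are also placed one baseline category too low.

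This rests on two conditions: the product is compared with the cut-off unrounded, since no rounding is stated, and the participant's total is exactly on the boundary. The documents do not say how many participants take these drugs at these doses. The number may be small, and nothing here shows that any result would change. The visible reach is secondary endpoints, one subgroup factor and baseline descriptions. Severity: minor.

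**What to change.** Three edits to SAP section 18.2:

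1. Table 6: replace 0.83333 by 1/1.2 for deflazacort, and 6.667 by 1/0.15 for dexamethasone and betamethasone, including the other entries that carry 6.667.
2. Table 7: state that the fraction column is the one applied and the decimals are for display.
3. Section 18.2.4: state that the summed daily dose is rounded to 0.01 mg before it is compared with any threshold or category boundary. This also protects against floating-point error.

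The cost is a few words in the SAP and a small change in the derivation program. No dose, taper rule or endpoint definition changes, and the analysis then agrees with the protocol's own equivalence table.

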18.2.4 Corticosteroid usage, daily dose

Prednisone-equivalent daily dose (mg) by visit (post-baseline visits):

• Prednisone-equivalent CS daily dose is equal to the total dose (mg) the participant is receiving at the date of the scheduled visit + 1 day (using conversion rules specified in section 18.2.3). If several CS are taken at the same scheduled visit, then all CS doses should be added.

CS dosing at Baseline is defined at CS dose taken the day of baseline visit (Day 1).

Signature Page for VV-CLIN-324916 v4.0

Approval Task	PPD
	13-Dec-2024 10:00:07 GMT+0000

Signature Page for VV-CLIN-324916 v4.0

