Appendix 7 Corticosteroids Guidance

In order to demonstrate the potential CS-sparing effect of enpatoran and its treatment effect compared with placebo, CS must be tapered as clinically tolerated.

[figure not shown]
This guidance applies to Cohort A and Cohort B participants.

Table 8 Corticosteroid Guidance for the Screening period and 24-Week DBPC period

Time period/Other	CS rules and guidance	Outcome if rules not followed
Screening period (prior to Day 1)	CS dosage must remain unchanged. Maximum prednisone-equivalent daily dose is 30 mg.	Screening failure and participant could be rescreened.
Day 1 visit to Week 2	CS dosage must remain unchanged. Maximum prednisone-equivalent daily dose is 30 mg/day.	
Week 2 (starting on Day 15) to Week 12	MUST taper CS to a target prednisone-equivalent daily dose of ≤ 5 mg/day at Week 12 or earlier, as clinically tolerated (see Table 1 for protocol-specified CS tapering guidance)	
Week 12 to Week 24	CS dosage must remain unchanged (i.e., initiation or increase is not allowed but decrease is permitted) since changes in CS may affect the clinical endpoints (e.g., BICLA response, CLASI-A reduction, CS-sparing effect, etc.).	
Week 24 to Week 26 (Safety Follow-Up)	CS dosage must remain unchanged.	
CS rescue	Allowed only once after Day 1 through Week 8: up to prednisone-equivalent daily dose of 30 mg or use 1 intramuscular CSR injection as rescue for worsening of SLE or CLE activity. The CS dose must be tapered within 7 days to ≤ CS dose used before the rescue (if not on any CS before the rescue, tapering within 10 days to prednisone-equivalent daily dose of 5 mg is allowed).	

Time period/Other	CS rules and guidance	Outcome if rules not followed
Injectable CS	CS injected intravenously, intra-articularly or SC are prohibited during the study (from the Screening Visit). CS injected intramuscularly after Week 8 are prohibited (only 1 injection allowed from Day 1 through Week 8).	
CS = Corticosteroids, EAC = Endpoi	nt Adjudication Committee.	

Figure 3 CS (prednisone-equivalent) dosing schedule

BICLA = BILAG-based Combined Lupus Assessment, CLASI = Cutaneous Lupus Erythematosus Disease Area and Severity Index, CS = Corticosteroids, FU = follow-up, LTE = Long-term extension, EAC = Endpoint Adjudication Committee.

Table 9 Corticosteroid Tapering Guidance during the 24-Week DBPC period (example only)

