In case the start date of study intervention is missing, it is assumed that the first dose of study intervention is given at the randomization date. The randomization date will replace incomplete dates of the first dose of study intervention.

Adverse events:

Incomplete AE-related dates will be imputed as follows:

- In case the onset date is missing completely or missing partially but the onset month and year, or the onset year are equal to the start of study intervention then the onset date will be imputed by the minimum of start of study intervention and AE resolution date (if not missing).
- In all other cases, the missing onset day or missing onset month will be imputed by 1.
- Incomplete stop dates will be imputed by the last day of the month (if day is missing only), if not resulting in a date later than the date of participant's death. In the latter case, the date of death will be used to impute the incomplete stop date.
- In all other cases, the incomplete stop date will not be imputed.

Previous and concomitant medication:

Incomplete previous/concomitant medication start and stop dates will be imputed as presented in Table 1Table 1.

For the derivation of previous and concomitant medications, the following rules will be applied:

37/125

Previous Medication:

- Start date ≤ Start of study intervention OR
- Start date = Missing

Concomitant Medication:

- End date ≥ Start of study intervention AND (Start date ≤ End of study intervention OR Start date=Missing) OR
- End date = Missing AND (Start date \le End of study intervention OR Start date = Missing)

Table 1 Imputation rules for missing/incomplete start/end dates of medication

	Start Date	End Date
Day missing only	Day = 1	Day = Last day of month
	Day = 1	Day = 31
Month missing	Month = Jan	Month = Dec
	Date = Missing	
Year missing	No imputation	
	if imputed date > date of death:	
All	imputation by date of death	

Concentration for pharmacodynamics/biomarkers:

For calculation of descriptive statistics, values below the lower limit of quantification will be set to half of the lower limit value (LLOQ). BLQ will be reported in participant data listings.

Missing data imputation related to the clinical efficacy questionnaires and efficacy estimands will be described in the corresponding sections.

In all participant data listings, imputed values will be presented, and imputed information will be flagged.

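### Partial corticosteroid dates are widened and the doses then summed, so consecutive steps of one taper can be added together in the steroid endpoints

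*SAP*

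**What the plan says.** Three SAP rules act in sequence.

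- **Dates (18.2.2):** "Start and end dates of CS medications will be imputed following the same rules as defined for the previous and concomitant medications". Those rules are in 9.10 Table 1. A start with unknown day becomes day 1, and with unknown month 1 January. An end with unknown day becomes "Day = Last day of month", and with unknown month 31 December. The only cap shown applies "if imputed date > date of death".
- **Daily dose (18.2.4):** the post-baseline dose is "the total dose (mg) the participant is receiving at the date of the scheduled visit + 1 day", and "If several CS are taken at the same scheduled visit, then all CS doses should be added". The baseline dose is the one taken on Day 1. Section 18.2.1 leaves a record out of the dose derivation only if its dose or frequency is missing or uninterpretable.
- **Use of the dose:** CS reduction (14.3.3) needs at least 10 mg at Day 1 and at most 5 mg by Week 12. After that, "Sustainment of the reduction will be assessed throughout the period between Week 12 and Week 24". BICLA plus CS reduction (14.3.4) uses the same test. LLDAS (14.3.7, at most 7.5 mg) and remission (14.3.8, at most 5 mg) apply their limits "from the day after the previous visit until the day of the current visit".

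Protocol Appendix 7 requires a taper from Week 2 to Week 12. From Week 12 to Week 24 it states that "initiation or increase is not allowed but decrease is permitted".

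**The concern.** A taper reaches the database as a chain of records of one drug at falling doses. Widening partial dates is a reasonable cautious choice for a yes/no concomitant flag. It does not suit a summed dose: the record that ended and the record that replaced it are both open until the imputed end date, and both are added. Nothing readable in the SAP makes the later record close the earlier one.

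At stake are four secondary endpoints in which one falsely high day can reverse a yes/no outcome, and entry to the population with at least 10 mg at Day 1. The protocol makes steroid sparing an explicit aim (6.8.1 and Appendix 7), and that aim is judged on this derived dose.

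**Working it through.** **Inputs.** Prednisone columns of protocol Table 9; SAP 9.10 Table 1; SAP 18.2.4. Study week w covers Days 7w+1 to 7w+7. Week 12 is Day 85, so its dose is read on Day 86. The Week 24 LLDAS/remission window is the day after Week 20 (Day 141) to Day 169, that is Days 142–169. Each calendar day of 2023 was taken in turn as Day 1 (365 dates).

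**1. Complete dates.** Every Table 9 column from 30 to 10 mg gives the plan's own 5 mg at Week 12, with 0% false failures on any criterion.

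**2. Worked case.** 30 mg column, Day 1 = 20 March 2023. The 7.5 mg step covers weeks 10–11 (29 May to 11 June) and 5 mg starts on 12 June. If the end of the 7.5 mg record is known only as June, it becomes 30 June. On 13 June (Day 86) the derived dose is 7.5 + 5 = 12.5 mg; the true dose is 5 mg.

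**3. How often the calendar allows this.** Let L be the last study day on 7.5 mg and k = 86 − L.

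- End day missing: the participant escapes only if L is in the last k days of its month, so the share failing is (365 − 12k)/365. For k = 30, only day 1 of the seven 31-day months fails.
- End month missing: CS reduction fails for (365 − k)/365. The Week 24 window fails for (365 − j)/365, where j = 142 − L.

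| Start dose | L | k | Day missing: CS reduction fails | j | Month missing: CS reduction fails | Month missing: Week 24 window fails |
|---|---|---|---|---|---|---|
| 30, 25 mg | 84 | 2 | 341/365 = 93% | 58 | 363/365 = 99.5% | 307/365 = 84% |
| 20, 15 mg | 77 | 9 | 257/365 = 70% | 65 | 356/365 = 97.5% | 300/365 = 82% |
| 12.5 mg | 63 | 23 | 89/365 = 24% | 79 | 342/365 = 94% | 286/365 = 78% |
| 10 mg | 56 | 30 | 7/365 = 2% | 86 | 335/365 = 92% | 279/365 = 76% |

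With only the day missing, the Week 24 window is never reached (0%), because j is at least 58 days and no month is that long. If every step lacks its day, the 30 mg column can stack to 15 + 12.5 + 10 + 7.5 + 5 = 50 mg at Week 12.

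**4. Late decreases.** A step from 5 to 2.5 mg with both days unknown gives 7.5 mg for the month. That fails sustained CS reduction, and fails remission if it falls in the window; LLDAS is still met. A step from 5 to 4 mg gives 9 mg and fails all three.

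**5. Same-day stop and start.** No imputation is involved. A 5 to 4 mg change counts as 9 mg on that day. The visit dose is protected by the one-day shift. The interval criteria are not protected for changes between visits, or on the current visit day for LLDAS and remission.

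**6. Day 1.** An old 7.5 mg record plus the current 5 mg record gives 12.5 mg, so a participant truly on 5 mg enters the population with at least 10 mg. The stable-dose rules (2 weeks before Screening, plus a Screening period of at least 2 weeks) mean that this usually needs a missing month. If the old record then runs to 31 December, the result depends on Day 1. Day 86 is Day 1 + 85 days, and 8 October + 85 days = 1 January. From 8 October onward the derived dose is back to 5 mg on Day 86, giving a false success; before that date it gives a false failure.

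**7. Illustration only.** Assume true CS-reduction rates of 50% versus 30%, a fraction q of responders in each arm with the critical end day missing, and a failing share f. The difference becomes 20 × (1 − qf) points: 19.7 for q = 2%, f = 0.70, and 16.3 for q = 20%, f = 0.93. These rates and q are assumptions, and false entries at Day 1 are ignored.

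**The case against.** The strongest reply is that 18.2.4 asks for the dose the participant is receiving, and that several CS most naturally means different steroids taken together. On that reading a sensible programmer would not add a superseded step. The reading is possible, but the text does not say which of two overlapping records of one drug is current, so it does not settle the derivation.

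The trigger may also be rare. On-study steroids have a dedicated eCRF form, taper schedules are collected, and the Medical Monitor and the EAC review CS use. This stands: the documents give no count of partial dates, and the impact may be small. The percentages above hold only if the critical date is partial; they are not expected failure rates.

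Two further limits stand. The one-day shift covers same-day changes made at a visit for the visit dose, and day-only gaps in an on-schedule taper do not reach the Week 24 LLDAS/remission window.

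A reader might infer that the error dilutes an enpatoran steroid-sparing effect, since successful taperers are the ones penalised. The documents do not support that. Tapering is required in every arm, so chained records arise in every arm, and stacking at Day 1 can create false successes.

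A reader might also extend the point to the primary endpoints. No visible text links this derived dose to CLASI-A or BICLA; for BICLA, non-compliant CS use is determined by the EAC (protocol Appendix 8).

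**Conclusion.** The concern holds in a limited form. Taken together, SAP 18.2.2, 9.10 Table 1 and 18.2.4 give a wrong daily dose for some participants with a partial CS date, because successive records of one steroid are not made exclusive. This is more than missing detail, since the rules as written produce the error.

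It can reverse CS reduction and BICLA plus CS reduction, LLDAS and remission at earlier visits, and, with a missing month or a late decrease, the Week 24 LLDAS and remission dose criteria. It can also admit a participant wrongly to the population with at least 10 mg. For an affected participant the error can be decisive (12.5 mg instead of 5 mg). For the trial its size is unknown, and its net direction between arms is not established. Secondary p-values are nominal (protocol 9.4). It should be corrected before lock because the remedy is cheap. The conclusion rests on the readable text; redacted passages and the interim analysis plan could not be seen.

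**What to change.** In SAP 18.2.2, replace the bare reference to 9.10 with a CS-specific rule for consecutive records of the same drug and route:

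- (a) Only the earlier end date partial: cap it at the day before the next record's known start.
- (b) Only the next start date partial: start it the day after the known previous end.
- (c) Both partial: use one changeover date, the latest consistent with both records. The earlier dose is carried until then and the two are never summed.
- (d) Stop date equal to the next start date: count only the new dose that day.
- (e) Course recorded as stopped before Day 1: cap its imputed end at the day before Day 1.

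Rule (c) matters because simply capping at an imputed start errs the other way. If both dates are known only as June, the next start becomes 1 June and the earlier dose is cut at 31 May. A true change on 25 June would then be scored as meeting a Week 12 visit on 12 June. Rule (c) is deliberately cautious: in the worked case with both dates partial it gives 7.5 mg on 13 June, not 12.5 mg, and still fails the 5 mg limit.

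In 18.2.4, state that doses are added only across different CS or truly concurrent prescriptions. Add a sensitivity analysis of the steroid endpoints for participants with imputed CS dates, for example earliest versus latest changeover, and report how many there are.

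Cost: a few lines of SAP text and a little extra programming. No new data and no protocol amendment are needed. With complete dates, or with rule (a) where only the end date is partial, every Table 9 schedule returns 5 mg at Week 12 and 0% false failures.
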